## 8.2. Follow-up

For prevalence estimations of individuals with recorded immunoglobulin prescriptions among the general study population (*objective 1*), individuals present in the data source between 1st of January 2017 and 31st of December 2024 will be included. For prevalence estimations among immunoglobulin users (*objective 2*), follow up will start on date of immunoglobulin prescription during the study period.

For patient-level drug utilisation (*objective 3*) and characterisation of individuals initiating immunoglobulin treatment (*objective 4*), follow-up of incident immunoglobulin users will start on the date of the first immunoglobulin prescription record of prespecified immunoglobulin brands during the study period. For primary care data sources, individuals are required to have 180 days data visibility prior to study inclusion and should not have a record of immunoglobulin prescription in the 180 days prior to study inclusion. For hospital care data settings, individuals are not required to have prior data availability, and no washout period will be applied prior to study inclusion. To ensure sufficient follow-up (*objectives 3–4*), only individuals with a first record of immunoglobulin prescription at least 180 days before the end of data availability in each data source will be included.

Follow-up (*objectives 1–4*) will end on the earliest of i) loss to follow-up, ii) death, iii) end of observation period (the latest available data), iv) or study end date 31/12/2024, whichever occurs first.

The code lists used to identify the start and end of follow-up determining events are presented in [Annex IV](#).

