### *Objective 2*

The study population will include all individuals who have a drug prescription or dispensing record of immunoglobulin and are present in the data source during the study period between 01/01/2017 and 31/12/2024.

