#### *Objective 2*

##### Inclusion criteria

- Present in the data source during the period of 01/01/2017 to 31/12/2024.
- Drug prescription or dispensing record of prespecified immunoglobulin brands during the study period.

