### 8.8.3. Statistical model specification and assumptions of the analytical approach considered

#### Objective 1

Trends of immunoglobulin use during the study period will be assessed based on OMOP CDM mapped data using the *IncidencePrevalence* R package (<https://github.com/darwin-eu/IncidencePrevalence>), developed by DARWIN EU®.

The prevalence of individuals with a recorded immunoglobulin prescription (expressed as the proportion of individuals with any immunoglobulin prescription in the general study population) will be presented by immunoglobulin ingredient, route of administration, and stratified by sex and age.

Prevalence will be calculated as overall and annual, which summarises the total number of individuals with recorded immunoglobulin use during a given period divided by the population at risk of receiving immunoglobulins during that period. Therefore, period prevalence will give the proportion of individuals exposed at any time during a specified interval. Binomial 95% confidence intervals will be calculated.

#### Objective 2

Trends of immunoglobulin use during the study period will be assessed based on OMOP CDM mapped data using the *IncidencePrevalence* R package (<https://github.com/darwin-eu/IncidencePrevalence>), developed by DARWIN EU®.

The quarterly prevalence of individuals with prescriptions for prespecified immunoglobulin brands will be estimated (expressed as the proportion of individuals prescribed each specific immunoglobulin brand among prevalent immunoglobulin users).

Prevalence will be calculated as quarterly period prevalence, which summarises the total number of individuals with recorded immunoglobulin brand prescription during a quarter divided by the population of prevalent immunoglobulin users during that period. Therefore, period prevalence will give the proportion of individuals exposed to a specific brand at any time during the specified interval. Binomial 95% confidence intervals will be calculated.

An illustration of the calculation of period prevalence is shown below in **Figure 3**. Between time  $t+2$  and  $t+3$ , two of the five study participants receive immunoglobulin treatment, giving a prevalence of 40%. Meanwhile, for the period  $t$  to  $t+1$  all five also had some observation time during the year with one of the five study participants having a recorded immunoglobulin prescription, giving a prevalence of 20%.

[figure not shown]

Figure 3. Prevalence example.

### Objective 3

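### The objective 2 denominator is contradicted in two ways: brand users or all immunoglobulin users, and users in the quarter or anyone still followed since a prescription

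*Protocol*

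**What the plan says.** **Who counts.** The abstract's objective 2 population is broad: "The study population will include all individuals who have a drug prescription or dispensing record of immunoglobulin". The objectives in Section 7, the design in Section 8.1 and the outcome list in Section 8.6.2 likewise place brand use among immunoglobulin users. The objective 2 inclusion criterion in Section 8.3 is narrower: "Drug prescription or dispensing record of prespecified immunoglobulin brands during the study period".

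**When they count.** Section 8.8.3 gives the calculation as "individuals with recorded immunoglobulin brand prescription during a quarter divided by the population of prevalent immunoglobulin users during that period". Section 8.2 says that for this objective "follow up will start on date of immunoglobulin prescription during the study period", and that follow-up for objectives 1 to 4 "will end on the earliest of i) loss to follow-up, ii) death, iii) end of observation period (the latest available data", or at the study end date of 31/12/2024. Stopping treatment is not among the end points. The visible note to Figure 1b repeats the same list.

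**The example.** The Figure 3 text, placed under objective 2 in Section 8.8.3, says "two of the five study participants receive immunoglobulin treatment, giving a prevalence of 40" per cent. For the other interval it again divides by all five, because all five had observation time, although only one had a prescription.

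**The concern.** A brand share is determined by its denominator, and quarterly brand prevalence is objective 2's listed output in Section 8.8.4. Two programmers following different sections would produce different figures, and the binomial confidence intervals would not reveal which denominator had been used.

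The two contradictions push in opposite directions. The Section 8.3 criterion removes immunoglobulin users who never have a listed brand, which raises the shares. The Section 8.2 follow-up rule, if it set the denominator, would keep former users in it while they remain under observation, which lowers the shares over successive quarters. Observation ends differently in the three sources (Section 9), so the second effect would differ by source and disturb comparison between countries.

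**Working it through.** **The plan's own figure.** 2/5 = 40% and 1/5 = 20%; both reproduce. Both divide by everyone with observation time, including people with no immunoglobulin in the interval. If the five are all immunoglobulin users, as objective 2 requires, this is a follow-up denominator and not an in-quarter one.

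**Contradiction 1: brand-only or any immunoglobulin.** Users without a listed brand can be expected. Table S3 lists ingredients such as palivizumab, nirsevimab, sotrovimab, tetanus and hepatitis B immunoglobulin, and Table S4 gives no brand for them. Keycute/Naxiglo is prespecified in Section 8.6.3 but has no entry in Table S4, and Section 9 accepts that some brands have no RxNorm code.

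Let u be the fraction of users in a quarter with no prespecified brand record in the study period. The numerator is unchanged and the denominator shrinks by (1-u), so shares rise by 1/(1-u):
- u = 20%: 1/0.8 = 1.25
- u = 50%: 1/0.5 = 2.0

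The protocol does not give u; these values are assumptions.

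**Contradiction 2: in-quarter users or everyone still followed.** Inputs from the protocol:
- Study period 2017 to 2024: 8 × 4 = 32 quarters.
- Median first observation period (Annex II): 116 days in IQVIA DA Germany, 247 in CDW Bordeaux, 2,150 in CPRD GOLD. These are whole-database values and serve only as proxies for exit after an immunoglobulin prescription.

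Assumptions: a constant true share of 30%, a constant number of new users per quarter, and exponential exit. Retention per quarter of 91.3 days is r = 0.5^(91.3/median). With one-off use, the quarter-k denominator relative to in-quarter users is S = 1 + r + … + r^(k-1), and the reported share is 30%/S. If half of new users continue until lost, it is 30% × (0.5 + 0.5/S).

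| Source | r | S at k = 32 | Nobody stops | Half continue | All one-off |
|---|---|---|---|---|---|
| IQVIA DA Germany | 0.58 | 2.38 | 30% | 21.3% | 12.6% |
| CDW Bordeaux | 0.77 | 4.42 | 30% | 18.4% | 6.8% |
| CPRD GOLD | 0.97 | 21.03 | 30% | 15.7% | 1.4% |

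The path over time matters as well. With one-off use:

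| Source | Quarter 4 | Quarter 8 | Quarter 16 | Quarter 32 |
|---|---|---|---|---|
| IQVIA DA Germany | 14.2% | 12.8% | 12.6% | 12.6% |
| CDW Bordeaux | 10.6% | 7.8% | 6.9% | 6.8% |
| CPRD GOLD | 7.8% | 4.1% | 2.3% | 1.4% |

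The first two sources show an early drop and then a plateau. Only CPRD GOLD declines throughout.

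**Cross-check with a different model.** Hold active users constant, let a proportion s stop and be replaced each quarter, and start from a 40% share. At s = 25%, the quarter-32 share is 29.8% (IQVIA DA Germany), 21.6% (CDW Bordeaux) and 6.7% (CPRD GOLD). At s = 0 it stays at 40%. The mechanism and the ordering agree.

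**With the in-quarter denominator**, the share stays at its true value in all 32 quarters under either model.

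**The case against.** The strongest defence is that Section 8.8.3 is the only place that defines the calculation, and its text is "divided by the population of prevalent immunoglobulin users during that period". Read as users in the quarter, nothing accumulates and there is no artefact. Section 8.2 describes follow-up, not a denominator. The worked example speaks of immunoglobulin treatment and of a year, which fits objective 1 better than a quarterly brand share, so it may be only a generic illustration.

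Much of this stands, and it rules out stronger conclusions that a reader might draw:
- *That brand shares will fall.* The fall occurs only if Section 8.2 and the example are coded in place of the Section 8.8.3 text. A brand whose true share is growing could still rise.
- *That every past user stays in.* Section 9 ends observation at the last recorded event in IQVIA DA Germany, the last visit in CDW Bordeaux and deregistration in CPRD GOLD. Only past users still observed accumulate.
- *That there are three incompatible denominators.* The abstract's study-period population and the quarterly users of Section 8.8.3 nest; the second can be a subset of the first.
- *That separate denominators by product class are required.* They would change the stated estimand, which is a share among all immunoglobulin users. Table S4 also maps Rhesonativ and Rhophylac partly to Immunoglobulin G concepts, so a Rho(D)-only denominator could miss people who are in the numerator.

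The defence does not settle the matter. The example sits inside Section 8.8.3, under objective 2, and departs from the text beside it. Nothing in the defence touches the Section 8.3 criterion, which conflicts with the stated objective on any reading.

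**Conclusion.** Two contradictions stand and should be resolved, because they bear on the quantity that objective 2 exists to report.

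The first applies if Section 8.3 is followed as written: wherever some users have no listed brand, shares are inflated by 1/(1-u) relative to the stated objective, with u unknown. The second is conditional: artificial decline arises only if the follow-up rule and the worked example set the denominator. Its size depends on stopping and exit rates that the protocol does not give, and it runs from no dilution to the one-off-use figures above. Those figures are an extreme case, resting on an assumed 30% share and on whole-database medians, and they illustrate the mechanism. They are not forecasts.

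**What to change.** - State the same quarterly denominator in Sections 8.2, 8.3 and 8.8.3: persons with at least one immunoglobulin record, of any listed ingredient and branded or not, in that quarter.
- Remove the brand requirement from the objective 2 inclusion criterion in Section 8.3.
- Move the worked example to objective 1, or replace it with one that counts only in-quarter users.
- Report a category for users with no prespecified brand recorded, so that u can be seen in each source.

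Shares within J06BA or Rho(D) users may be added as optional supplementary analyses; they are not part of the correction.

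The cost is wording in a few places and a quarter-specific denominator in the code. Quarterly denominators will be smaller, and intervals wider, than under the accumulating reading.

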#### *Objectives 3–4*

##### Inclusion criteria

- Present in the data source during the period of 01/01/2017 to 31/12/2024.
- Minimum 180 days of available history before index data. This criterion does not apply for hospital data source CDW Bordeaux.
- First drug prescription or dispensing record of prespecified immunoglobulin brand during the study period.
- No prior immunoglobulin exposure in the 180 days prior to the index date. This criterion does not apply for hospital data source CDW Bordeaux.

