To ensure comprehensive characterisation of all incident individuals, a minimum of 180 days of prior data availability is required for primary care data sources. This criterion may reduce the study size and will not be applied for hospital-based settings, where patients typically seek care for acute or specialised conditions and might, as a result, not have a long duration of longitudinal registration, as would be expected in a primary care setting data sources. Consequently, for CDW Bordeaux, it is uncertain whether included individuals are true incident users. Moreover, only a subset of included patients from hospital-based settings may contribute to time windows prior to the index date. The prior observation requirement may also imply selection bias favouring chronic indications, i.e., data in some pathological conditions may be limited or absent.

Of note, certain brands of interest cannot be assessed in the current study due to limitations, such as market authorisation occurring after the study period or the unavailability of an RxNorm code for those specific brands.

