## 11. ANNEXES

### ANNEX I. Description of data sources

#### DATA SOURCES DESCRIPTION

##### France: Clinical Data Warehouse of Bordeaux University Hospital (CDW Bordeaux)

#	Section	Description
1	Database Identification and country	CDW Bordeaux (Clinical Data Warehouse of Bordeaux University Hospital) Nouvelle-Aquitaine, France
2	Data partner information section	CHU DE BORDEAUX - DIRECTION GENERALE Gironde / Nouvelle-Aquitaine
3	Coverage and timespan	Data collection since 2005 Extent: Regional. It covers the population of Bordeaux metropolitan area, and possibly beyond, as the health care centre for referrals and expertise for the Nouvelle Aquitaine region. The database contains data from 2005 onwards.
4	Healthcare setting / type of data	Secondary care – specialists (ambulatory or hospital outpatient care), and hospital inpatient care, and claims data. The database currently captures information about patient demographics, visit details, conditions, procedures, drugs, measurements, and mortality.
5	Data collection process	Outpatient electronic health records, and Inpatient hospital electronic health records, and Inpatient hospital billing systems, and Biobank. The integrated data is extracted from the hospital production information system via a real-time research database. The data is then processed and quality controlled by a team dedicated to maintaining the database. Internal evaluations were carried out to ensure consistency between the research database and the patient bedside software.
6	General representativeness	This is the 6th largest metropolitan area in France, and CHUBX is the largest hospital in the region. More than 75% of the patients administered to Bordeaux university hospital reside in the Gironde departments, with almost 50% coming directly from the Bordeaux metropolitan area. The hospital also captures additional cases from Nouvelle-Aquitaine region.
7	Data content /source coding	Diagnosis source data is coded in ICD-10 terminology. Procedures are coded in CCAM (French terminology). Laboratory measurements are coded in local terminology and partially mapped to LOINC. Drugs are coded through a local terminology and then mapped to UCD (French terminology), as well as ATC codes.

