## ANNEX II. Fitness for use assessment

### Data source justification for inclusion and key characteristics

#### **France: Clinical Data Warehouse of Bordeaux University Hospital (CDW Bordeaux)**

CDW Bordeaux will be included in this study because it is a hospital data source that provides relevant information on the use of immunoglobulins in the general population.

Based on a preliminary feasibility assessment, the expected number of person counts for immunoglobulin use in CDW Bordeaux will be 10,900.

Moreover, data availability and follow-up in CDW Bordeaux is sufficient, as data availability starts in 2005, and the date of most recent data extraction is 09/2025, which aligns with the study period. The median follow-up of the first observation period is 247 days.

There are no study specific limitations present in CDW Bordeaux.

Lastly, IRB approval for CDW Bordeaux is estimated to take 1 to 2 weeks, which makes the execution of this study feasible within the current study timelines.

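### For CDW Bordeaux the check for recent immunoglobulin use is waived along with the prior-history requirement, so patients with a recorded recent exposure are reported as initiators

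*Protocol*

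**What the plan says.** Objectives 3 and 4 concern people starting treatment. Section 8.2 calls them incident users, section 8.6.2 refers to initiators, and the shells for Tables 4 to 8 in section 8.8.4 describe every included patient as initiating or having initiated therapy.

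Section 8.3 lists two separate entry criteria, each with its own exception for the hospital source:

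- History: "Minimum 180 days of available history before index data. This criterion does not apply for hospital data source CDW Bordeaux".
- Prior use: "No prior immunoglobulin exposure in the 180 days prior to the index date. This criterion does not apply for hospital data source CDW Bordeaux".

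Section 8.2 waives both in one sentence, dropping the need for prior data in hospital sources and adding that "no washout period will be applied prior to study inclusion". The abstract, the footnote to Figure 2, section 8.6.1 and section 8.8.3 likewise limit the washout to the primary care sources. The Table 2 attrition shell keeps history and prior use as separate rows and enters NA for CDW Bordeaux in both.

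Section 9 explains the waiver and concludes: "Consequently, for CDW Bordeaux, it is uncertain whether included individuals are true incident users". On what the source holds, Annex I states "The database contains data from 2005 onwards" and "The database currently captures information about patient demographics, visit details, conditions, procedures, drugs, measurements, and mortality".

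**The concern.** The two criteria ask different things of the data. The history criterion requires that a patient was observable for 180 days. The prior-use criterion requires only that no immunoglobulin record exists in that window, and it can be applied to whatever records there are. Waiving both in Bordeaux keeps patients whose earlier treatment is visible in the same database and labels them initiators.

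CDW Bordeaux is the only hospital source, and section 9 notes that intravenous products are given mainly in hospital. For a patient already on treatment, the reported initial dose is a dose from the middle of a course. The [-7, +7] and [-30, +7] indication windows surround a continuing treatment. The infections and antibiotics in [0, +30] and [0, +365] are those of an established user. The shells also place Bordeaux beside two sources in which such patients have been removed, so the columns describe differently selected groups under one label.

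**Working it through.** The plan gives no figure of its own on this point, so the check covers the rules, the dates and an illustrative range.

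**1. Which waiver does the stated reason support?** Section 9 argues that hospital patients often come for acute or specialised care without long registration, and that requiring 180 days of prior data may shrink the cohort. Its worry about favouring chronic indications is also tied to prior observation. All of this concerns missing history. A check on existing records has no such effect: a patient first seen on the index date has no earlier record and passes. No reason is given for waiving the prior-use criterion on its own.

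**2. Is there a look-back?** Inputs: data from 2005 (Annexes I and II; 1 January assumed), study start 01/01/2017 (section 8.5), window 180 days (section 8.3).

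- Coverage before study start: 12 × 365 + 3 leap days = 4,383 days, and 4,383 / 180 ≈ 24 windows.
- Window for the earliest possible index date: 01/01/2017 − 180 days = 05/07/2016, well after the warehouse starts.

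**3. One patient under the two rules.** Take recorded immunoglobulin on 15/12/2016 and a prespecified brand on 12/01/2017, 28 days apart, with at least 180 days of history.

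| Criterion (section 8.3) | Germany, UK | CDW Bordeaux |
|---|---|---|
| First prespecified-brand record in study period | met, 12/01/2017 | met, 12/01/2017 |
| 180 days of history | met | not applied |
| No immunoglobulin in prior 180 days | failed | not applied |
| Result | excluded | counted as an initiator |

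Section 9 says Bordeaux patients are observed from first to last visit, so both records fall within the observed span. The problem is not confined to early 2017. A patient treated in any study year with an immunoglobulin that is not on the brand list, and then with a listed brand, also enters as an initiator.

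**4. Size.** The protocol does not give the share p of Bordeaux patients with a record in the 180 days before index. The feasibility count is 10,900 persons with any immunoglobulin (Annex II). This is not the number of brand initiators in 2017–2024, which can be expected to be smaller. Purely as an assumption, number removed = 10,900 × p:

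| p | Removed | Left |
|---|---|---|
| 2% | 218 | 10,682 |
| 5% | 545 | 10,355 |
| 10% | 1,090 | 9,810 |
| 20% | 2,180 | 8,720 |
| 30% | 3,270 | 7,630 |

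**The case against.** The strongest reply is that the choice is deliberate, consistent and disclosed. The waiver is stated the same way throughout, the abstract describes the hospital population simply as people with an immunoglobulin record, and section 9 warns that incident status is uncertain. It is true that the protocol neither contradicts itself nor hides the waiver. But section 9 presents the uncertainty as a consequence of missing history. For a patient with a record weeks before index there is no uncertainty, and nothing tells the reader that such patients are kept. Annex II adds that CDW Bordeaux has no study-specific limitations.

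Three further objections have force and shape the remedy:

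- A check on records alone screens unevenly. It removes users known to this hospital and keeps equally established users referred from elsewhere, so the section 9 caveat would still be needed.
- The ingredient list in Table S3 includes tetanus immune globulin, palivizumab, sotrovimab and casirivimab. Applied in full, it would exclude a true starter of a normal immunoglobulin who had recently received one of these.
- Annex I says that drugs are currently captured, not that drug records reach back to 2005, and duplicate identities were reprocessed only from 2015. The look-back is therefore plausible rather than documented, although the check needs records only from July 2016.

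**Conclusion.** The point holds as a design weakness that should be corrected. The no-prior-use check is waived for CDW Bordeaux without a reason of its own, and the initiator label is kept for patients whose recent use may be on record. This rests on the section 8.3 criteria as written and on immunoglobulin records being available from mid-2016, which the data partner should confirm. The size is unknown.

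Three stronger readings are not supported:

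- A reader might estimate the carried-over share as D/(8 + D) for a mean treatment duration of D years over eight entry years, giving 0.5/8.5 ≈ 6% at D = 0.5 and 5/13 ≈ 38% at D = 5. The protocol gives no D and no basis for a steady state. The formula also counts all carried-over users, not those with a record in the 180-day window and a later prespecified-brand record at this hospital.
- A reader might infer that every brand switcher becomes an initiator of the new brand. That follows only if the index date is set per brand. Results are reported per brand, but sections 8.2 and 8.8.3 can also be read as one index date per person.
- A reader might infer that a washout would make the Bordeaux cohort truly incident. It would not, because treatment given elsewhere stays unseen.

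**What to change.** Keep the history waiver for CDW Bordeaux and remove the second exception: exclude patients with a recorded immunoglobulin in the 180 days before index, with no minimum observation required.

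State which concept list the check uses, preferably the same one for all three sources. One option is the prespecified brands plus the normal immunoglobulin ingredients, so that an unrelated specific immunoglobulin or monoclonal antibody does not exclude a true starter. State also whether the index date is per person or per brand.

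In the Table 2 shell, replace NA in the prior-use row for Bordeaux with the number removed. Amend the abstract, the Figure 2 footnote, and sections 8.2, 8.3, 8.6.1 and 8.8.3 (objectives 3 and 4) to match. Keep the section 9 caveat and reword it to say that prior use outside this hospital cannot be screened.

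The cost is a smaller Bordeaux cohort, screening that remains incomplete, and a small change to the cohort code. If the sponsor prefers to keep the current cohort, the minimum is to report how many Bordeaux patients have a record in the prior 180 days, show the objective 3–4 results without them, and relabel the cohort as users at first record in the study period.
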